#### Peri-Implant Diseases

In the last decades, replacement of teeth with dental implants became a very frequent procedure, and it is associated with high rates of implant survival (Albrektsson and Donos, 2012). However, the incidence of technical and biological complications seems to be frequent (Scwartz et al., 2018). Since the number of subjects receiving dental implants is growing continuously (Schimmel et al., 2017), preventing and effectively resolving peri-implant diseases on the long-term without compromising esthetic results have become one of the major endeavors of this field.

In 2017, the World Workshop jointly held by the European Federation of Periodontology and the American Academy of Periodontology on the classification of Periodontal and Peri-Implant Diseases, defined peri-implant disease as a pathological condition occurring in tissues around dental implants, characterized by inflammation in the peri-implant connective tissue (ie, peri-implant mucositis - PM), and progressive loss of supporting bone (ie, peri-implantitis - PI) (Schwarz et al., 2018). The onset of peri-implant diseases is characterized by the presence of etiological factors similar to those involved in the etiology of periodontal diseases and it might occur within the first three years of function in a non-linear and accelerating pattern (Derks et al., 2016).

A recent systematic review and meta-analysis, performed by Jan Derks and colleagues in 2015, found a prevalence of 43% for PM and 22% of PI. Later on, in Spain, Rodrigo et al. (2018) observed similar PI prevalence's with 24% of the subjects presenting bleeding on probing and radiographic bone loss  $\geq$  2mm after at least 5 years of function.

The predictability of treatment of PI remains controversial, with evidence of results from several controlled clinical studies pointing out that nonsurgical treatment appears to be unpredictable with potential beneficial clinical outcomes limited to a period of 6–12 months (Renvert et al., 2008). However, in the last years, two 12-month follow-up case studies demonstrated a novel protocol to address PI, with improved outcomes (Stein et al., 2018; Nart et al., 2019). Notwithstanding the above, at the moment, surgical treatment is still the standard of care, with a resective or regenerative approach depending on the morphology and anatomy of

## SPECIFIC COMMISSION OF THE DOCTORAND

the bone defects resulting from the disease (Claffey et al. 2008). In spite of that, the predictability and long-term stability of these procedures are still a matter of controversy (Teughels et al., 2006; Renvert et al., 2012; Chan et al., 2014; Serino et al., 2015). Therefore, efforts from the research community should be more directed towards prevention.

### **Compliance to supportive periodontal therapy and prevention of peri-implantitis**

In the 3rd World Workshop, all the efforts taken after completion of the dental implant therapy were defined as supportive periodontal therapy (SPT), as opposed to periodontal maintenance, to highlight the importance of this phase of treatment. Moreover, in the same workshop, factors such as patients with history of chronic periodontitis, poor bacterial plaque control skills, and absence of regular maintenance care after implant therapy were recognized as being more likely to develop peri-implant diseases (Schwarz et al., 2018). This stress the idea that SPT is mandatory to prevent future breakdown of the disease.

The rational for doing SPT is due to three main facts: i) bacterial plaque and its byproducts represent the primary etiological factor for further breakdown (Lang et al., 2008); ii) after being exposed to inflammation, tissues are more susceptible due to changes in gene expression that are not encoded by DNA itself (Martins et al., 2016); iii) recolonization with putative bacteria such as spirochetes and motile rods occurs as soon as 4 to 8 weeks after active periodontal treatment (Mousques et al., 1980; Magnusson et al., 1984), highlighting the importance of frequent disruption of the biofilm.

In this context, SPT can determine the failure to meet oral hygiene standards (Morrison et al., 1979). Several studies conducted in the 1980's have clearly demonstrated that long-term therapeutic outcomes can be achieved if patients practice good oral hygiene and enroll in a regular supportive periodontal treatment after active periodontal therapy (Becker et al., 1984a; Becker et al., 1984b; Axelsson et al., 2004). Moreover, other studies concluded that without effective oral hygiene skills and a regular SPT program, the beneficial effects of various periodontal therapies would be compromised (Nyman et al., 1977; Axelsson et al., 1981).

Nevertheless, even though SPT is considered to be crucial to maintain peri-implant health, classic studies have shown that patient's adherence to SPT is not satisfactory (Wilson et al., 1984). Several studies have been carried out in different settings involving a considerable variety of cohorts of patients coming from both university and private practices in order to assess the factors that are associated with the lack of compliance with SPT (Ramseier et al., 2014, Perrell-Jones and Ireland, 2016). Identifying patients who are more likely to present a non-compliant pattern would help clinicians to focus their attention on these particular subjects, who mostly require a motivational strategy tailored to each individual risk profile (Amerio et al., 2019). The same publication pointed out that smoking habit and history of periodontal disease were found to be associated with patients' compliance. Inadequate information/motivation was found as the main patient-reported reason for non-compliance.

Addressing the main reason for patients' non-compliance is a research priority; however, studies in the literature are scarce. It's crucial that clinicians understand the importance of supportive periodontal treatment to prevent the development and progression of peri-implant diseases (Schwarz et al., 2018). Therefore,

## SPECIFIC COMMISSION OF THE DOCTORAND

missing or inadequate information given to patients after finishing the active periodontal treatment or the dental implant therapy is condemned to end. Patient motivation, nevertheless, is something external and depends mainly on patients' psychological factors and personality traits (Komarraju et al., 2009). The main reason is going to be addressed in the first part of this research project. The second most frequent reason for patients to fail SPT on these questionnaires was **bad experiences and dissatisfaction**. It has been demonstrated that peri-implant probing, even in healthy tissues, caused significantly more pain/discomfort than periodontal probing (Ringeling et al., 2016; Stanner et al., 2017; Parvini et al., 2017). Such finding might be due to: 1) differences between periodontal and peri-implant tissues or, 2) on average, higher levels of inflammation are observed around dental implants than around teeth (Meyer et al., 2017).

Considering these premises, one might suspect that a SPT visit to the dental office can be associated with a bad experience (Si et al., 2016), especially when these patients have one or more implants. Several debridement methods have been associated with better experiences around teeth. Less treatment discomfort was reported when comparing laser therapy with conventional therapy (Tomasi et al., 2006; Ratka-Kruger et al., 2012). Also, around teeth, air-polishing devices (APD) has been described as being significantly more comfortable and less painful than conventional instrumentation (Petersilka et al., 2003a; Petersilka et al., 2003; Möene et al., 2010; Wennström et al., 2011; Muller et al., 2014). An erythritol based air-polishing powder (Electro Medical Systems, Nyon, CH) have been recently introduced as a low abrasive powder (Hagi et al., 2013). Erythritol is a polyol used in food industry as an artificial sweetener. Its physical properties were shown to be comparable to glycine (Hagi et al., 2015). Moreover, when used during SPT, similar results in terms of clinical and microbiological outcome were demonstrated in comparison with hand instrumentation (Hagi et al., 2015). The efficacy of APD as monotherapy around dental implants, in the treatment of peri-implant diseases, have been addressed in a recent systematic review (Schwarz et al., 2015) – comparable results were found between conventional devices and APD in terms of mucositis treatment and better outcomes regarding peri-implantitis. However, only one of the studies included in the review observed that “no complains or discomfort” were reported by any of the patients investigated (Ji et al., 2014) – even though, no visual analog scale or other measurement scale was used for this purpose.

To our knowledge, only one study compared pain/discomfort during SPT around dental implants (Menini et al., 2019). This study included only full-mouth implant-supported restoration and compared three debridement approaches: 1) glycine air polishing; 2) sodium bicarbonate air polishing and, 3) manual scaling with carbon-fiber cures. Since they didn't use a control group with ultrasonic devices, and no teeth were included in the study, it reduces its external validity. Nevertheless, they observed statistically significant better VAS scores for glycine group when compared with sodium bicarbonate air polishing. Leading to a possible effect of the size of the powder particles in the pain perception, which could be improved with the erythritol due to its even smaller particle size (Hagi et al., 2013).

### **2. Background and current status of the topic:**

Implants have become a popular and widely used treatment option for treating partial and total edentulism. As the number of implants placed increases, so does the incidence of peri-implant mucositis and peri-

## **SPECIFIC COMMISSION OF THE DOCTORAND**

implantitis. Placing patients under SPT/maintenance care has been shown to prevent and treat such conditions. Despite SPT's importance in prevention and infection control, adherence to scheduled SPT visits have been unsatisfactory. Understanding the reasons for non-compliance can help both the clinician and research community to address them by improving communication and/or patients experience to those visits thereby increasing compliance.

### **3. Objectives:**

#### a) General objective

Evaluate the patient reported outcomes to a different implant instrumentation method during SPT visits, as well as its impact in compliance rates.

#### b) Specific objective

1. To evaluate pain/discomfort during SPT around dental implants and teeth.
2. To evaluate patient reported outcomes and clinical variables by decontamination during SPT with erythritol based air polishing powder (Air Flow Master®, Air-Flow Plus®, EMS, Nyon, Switzerland), at the first SPT and after 2 years.
3. To evaluate the effect of erythritol based air polishing powder (Air Flow Master®, Air-Flow Plus®, EMS, Nyon, Switzerland) during SPT on the compliance rates after 1 and 2 years of follow-up.

### **4. Hypothesis:**

#### a) General Hypothesis

The proposed protocols, focused on the prevention of peri-implantitis, will result in an increase adherence to SPT by better understanding the specific factors related to non-compliance, specifically by improving the experience of patients to SPT visits.

#### b) Specific Hypothesis

1. SPT with conventional ultrasonic device will result in more pain/discomfort around dental implants than in teeth.
2. SPT by means of an erythritol based air-polishing powder (Air Flow Master®, Air-Flow Plus®, EMS, Nyon, Switzerland) will result in better patient reported outcomes and same clinical outcomes, at the first SPT and after 2 years.
3. SPT by means of an erythritol based air-polishing powder (Air Flow Master®, Air-Flow Plus®, EMS, Nyon, Switzerland) will result in the increase of the compliance rates after 2 year of follow-up.

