### ***Sample Size Calculation***

The sample size will be calculated using changes in CAL as the primary outcome variable. Thirty patients (15 subjects in each group) were necessary to detect a difference of  $\geq 1$  mm in CAL assuming a mean standard deviation (SD) of 0.9. This calculation assumes an alpha error of 0.05, a beta error of 0.2, and a statistical power of 80%. In addition, 12% of loss to follow-up was considered.

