### **Screening examination**

The clinician will review with the patient the Information and Medication History Forms and record the anthropometric, socio-demographic and clinical information. Candidates will undergo an oral pathology examination and a full-mouth manual probing using a periodontal probe PCP-UNC 15 (HuFriedy®, [name]) to determine their periodontal and peri-implant status. Presence or absence of plaque will be recorded after staining with an erythrosine disclosing dye (Plac-Control®, Dentaid SL, Cerdanyola, Spain). Finally, periapical radiographs (Dürr Dental AG, Bietigheim-Bissingen, Germany) of all implants will be taken using a paralleling cone technique and a film-holder (7mA- 60kV/20ms).

The same calibrated examiner ([name]) will record clinical variables of mPI, BOP, PPD, MR and clinical attachment level (CAL).

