#### **Secondary outcome;**

- *Changes in the following clinical variables: FMPI, FMBI, PPD, GR, mPI, mBI, SOP, Implants PPD and MR after decontamination during SPT.*
- Compliance to SPT reported after decontamination during SPT.

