### ***Withdrawal of consent***

The Patient Information Sheet will clearly state that the patient can withdraw from the study at any time without prejudice or explanation. Such withdrawal will be documented in the medical record file. Losses to follow-up are taken into account in the sample size calculations (12%).

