### ***Statistical analysis***

#### *Descriptive analysis*

Descriptive statistical methods (percentage and numbers on total) will be used to analyze the evaluated parameter

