#### *Inferential analysis*

Data will be calculated at patient level and implant/tooth level. VAS score will be considered as the main outcome (quantitative).

If the distribution is normal, the following tests will be used:

- Binary categorical variables: T-Student / Fisher's exact test;
- Categorical variables with > 2 categories: ANOVA;
- Quantitative variables: Simple linear regression / Pearson correlation coefficient.

If it doesn't follow normality:

- Binary categorical variables: U of Mann-Whitney;
- Categorical variables > 2 categories: H of Kruskal-Wallis;
- Quantitative variables: Spearman's correlation coefficient.

[figure not shown]

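### Hypothesis 2 predicts the same clinical outcomes in both arms, but the only evidence the planned analyses could offer for this is a non-significant test of difference

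*Combined protocol and SAP*

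**What the plan says.** Specific Hypothesis 2 predicts that the test method "will result in better patient reported outcomes and same clinical outcomes, at the first SPT and after 2 years".

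The clinical variables concerned are listed under Secondary outcome, as changes in "FMPI, FMBI, PPD, GR, mPI, mBI, SOP, Implants PPD and MR after decontamination during SPT". The main outcome is pain/discomfort on the VAS.

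Under Descriptive analysis, "Descriptive statistical methods (percentage and numbers on total) will be used to analyze the evaluated parameter". Under Inferential analysis, "Data will be calculated at patient level and implant/tooth level". The methods named there for normal data are the t-test or Fisher's exact test, ANOVA, and simple linear regression or Pearson correlation. For non-normal data they are Mann-Whitney ("Binary categorical variables: U of Mann-Whitney"), Kruskal-Wallis and Spearman.

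Sample Size Calculation gives 30 patients, 15 per group, to detect a difference of at least 1 mm in change in clinical attachment level (CAL), with SD 0.9, alpha 0.05 and 80% power. It adds: "In addition, 12% of loss to follow-up was considered". Withdrawal of consent repeats the 12%. CAL is recorded at the screening examination but is not among the nine clinical variables listed as secondary outcomes.

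**The concern.** The two halves of Hypothesis 2 need different kinds of evidence. Tests of difference suit the patient-reported half. They cannot support the clinical half, because failing to reject equality does not show equality. Every inferential method named is a test of difference or a measure of association. Regression could yield an interval, but the plan asks for none. The readable text contains no margin, interval criterion or other rule for concluding 'same'.

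In a trial of this size, a non-significant clinical comparison is the likely result both when the methods perform alike and when the test method is moderately worse. The natural summary of a favourable trial would be less pain at no clinical cost. If its second part rested on non-significance alone, it would claim more than the data show.

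**Working it through.** **1. The plan's own figure.** Inputs from Sample Size Calculation: difference 1 mm, SD 0.9, alpha 0.05 (two-sided assumed, as sidedness is not stated), power 80%, loss 12%.

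n per arm = 2 × 0.9² × (1.960 + 0.842)² / 1² = 12.7, so 13. Allowing for loss, 13 / 0.88 = 14.8, so 15 per arm and 30 in total.

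The figure reproduces. It is a calculation to detect a difference, and it suggests that the 30 already includes the 12%. I therefore take 15 per arm at the first visit and 15 × 0.88 = 13.2, about 13, at 2 years.

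**2. Precision in SD units**, for a roughly normal patient-level outcome. Half-width of the 95% CI = t(0.975, 2n−2) × √(2/n), in SDs of the variable analysed:

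- n = 15: 2.048 × 0.365 = 0.75 SD
- n = 13: 2.064 × 0.392 = 0.81 SD

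**3. How often a real deficit is non-significant.** P(p>0.05) = 1 − power of the two-sided t-test, from the noncentral t distribution with noncentrality d × √(n/2). For d = 0.5 this is 1.37 (n = 15) and 1.27 (n = 13).

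| True deficit | 15 per arm | 13 per arm |
|---|---|---|
| 0.5 SD | 74% | 77% |
| 0.75 SD | 49% | 55% |
| 1.0 SD | 25% | 31% |

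The documents give no SD and no important difference for any of the nine variables, so these deficits are a range and not a judgement of what matters clinically.

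**4. The one scale with an SD in the plan.** For CAL (SD 0.9 mm; illustration only) the half-width is 0.9 × 0.748 = 0.67 mm with 15 per arm and 0.9 × 0.810 = 0.73 mm with 13.

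- A true deficit of 0.5 mm gives p>0.05 in 69% (15 per arm) to 73% (13 per arm) of trials. A deficit of 1 mm does so in 16% to 22%.
- If there is truly no difference, the 95% CI excludes a 1 mm deficit in 84% (15 per arm) to 78% (13 per arm) of trials. It excludes a 0.5 mm deficit in only 31% to 27%.

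**5. What baseline adjustment adds.** The plan already defines the clinical outcomes as changes, so the fair comparison is with change scores. Assume equal SDs at both times and baseline correlation r, and express half-widths in SDs of the follow-up value.

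- Change score: t(0.975, 2n−2) × √(2/n) × √(2(1−r))
- Adjusted for baseline: t(0.975, 2n−3) × √(2/n) × √(1−r²)

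| r (assumed) | Change score, n = 15 to 13 | Baseline-adjusted, n = 15 to 13 |
|---|---|---|
| 0.3 | 0.89 to 0.96 | 0.71 to 0.77 |
| 0.5 | 0.75 to 0.81 | 0.65 to 0.70 |
| 0.7 | 0.58 to 0.63 | 0.54 to 0.58 |

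Adjustment gives a narrower interval in each row, with little gain when the correlation is high.

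**The case against.** The strongest reply is that 'same' is only an expectation. Specific objective 2 is to evaluate the clinical variables, not to show that they are equal. The variables are secondary, the main outcome is a superiority question that the listed tests fit, and no equivalence or non-inferiority objective is declared. All of this stands, and it limits the point. A reader might infer that the sponsor intends to treat p>0.05 as proof of equivalence, or that this is an equivalence trial with too few patients. The documents support neither reading: no such rule is written, and without a margin or an SD for the listed variables no sample size can be called inadequate for that purpose.

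A second reply is that the CAL interval is narrower than the 1 mm the plan names, so the design could serve a claim at that margin. The arithmetic is right. But the plan presents 1 mm as a difference to detect and not as a margin, and CAL is not a listed outcome.

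Third, several outcomes are far from normal: suppuration (SOP) is present/absent, mBI is dichotomised and mPI is a 0 to 3 score. This also stands. The SD-unit figures should not be carried over to SOP or dichotomised mBI.

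None of these replies supplies an inferential route to the clinical half of Hypothesis 2.

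**Conclusion.** The point holds as a mismatch between a stated hypothesis and the analyses planned for it. If the plan is followed as written, nothing but non-significance could be offered for 'same', and non-significance would be expected in about three trials in four with a true deficit of 0.5 SD. On the CAL scale, a 1 mm deficit could usually be excluded if there were truly none, but a 0.5 mm deficit usually could not.

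These sizes assume roughly normal patient-level outcomes, unadjusted two-sided tests at 0.05, and 15 then about 13 evaluable patients per arm. If the 30 were instead meant as completers, enrolment would be 15 / 0.88 = 17.05, so 18 per arm. The half-width at the first visit would then be 2.032 × √(2/18) = 0.68 SD, which does not change the conclusion. One figure after the inferential section is not shown, so the verdict rests on the readable text.

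The change should be made before analysis. It does not call the main VAS comparison or the sample-size arithmetic into question.

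**What to change.** 1. Reword Specific Hypothesis 2 so that it does not claim 'same'; for example, say that clinical outcomes will be estimated and compared between arms.
2. For each of the nine listed clinical variables, report the patient-level test-minus-control difference with a 95% CI at the first visit and at 2 years. Define the patient-level summary in advance, for example the mean over sites for PPD, GR, MR and mPI.
3. For quantitative outcomes, adjust for the baseline value. Screening examination does not name every variable, but outcomes defined as changes already require a baseline.
4. For SOP and dichotomised mBI, use a difference in patient-level percentages with an interval suited to sparse data.
5. State that a non-significant result will not be read as sameness.

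A non-inferiority claim is not required. If one is wanted, it needs a named listed variable, a justified margin set in advance, a CI rule and the power at that margin. It may also need more patients; how many cannot be derived from the documents.

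Cost: no new patients, visits or measurements, some rewording, and a little more analysis, including models that the statistical section does not list. The real downside is that the sponsor may be unable to claim 'same' clinical outcomes.

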## **5. Materials and Methods:**

### ***Study Design***

The present research project is designed as a randomized controlled double-blind clinical trial with a 2-year follow-up. The reporting of this clinical trial will follow the Consolidated Standards of Reporting (CONSORT) guidelines. It is registered in ClinicalTrials.gov (...)

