### **VAS**

After finishing the supragingival debridement around teeth, another calibrated examiner ([name]) will give the patients graded pain intensity on a visual analogue scale (VAS) (0 = no pain and 10 = extreme, unbearable pain), and then perform supragingival debridement around the dental implants and give VAS again. Patients will be instructed to point at the VAS.

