### **Follow-up visits**

Patients enrolled in the study will be called for supportive periodontal therapy considering their SPT program and supragingival debridement will be performed accordingly to their group (control or test). All clinical variables will be re-examined by the same blinded examiner ([name]) after the first SPT visit, at 1 year and 2

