### ***Outcomes of the study***

#### **Main outcome;**

- Patient Pain/Discomfort (VAS) reported after decontamination during SPT.

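### The trial is called double-blind, but no masking is described for the between-arm comparison of its main outcome, the patient-reported VAS

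*Combined protocol and SAP*

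**What the plan says.** All references are to the combined protocol and SAP.

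- **Label.** Study Design: "randomized controlled double-blind clinical trial with a 2-year follow-up". The blinded parties are not named.
- **Who is blinded.** Follow-up visits: "All clinical variables will be re-examined by the same blinded examiner". No other section calls anyone blinded.
- **Main outcome.** Outcomes of the study: "Patient Pain/Discomfort (VAS) reported after decontamination during SPT". Inferential analysis agrees: "VAS score will be considered as the main outcome (quantitative)". The clinical variables are listed as secondary.
- **Direction expected.** Specific Hypothesis 2: the test device "will result in better patient reported outcomes and same clinical outcomes, at the first SPT and after 2 years".
- **Procedures.** Under Debridement, control patients receive an ultrasonic device, with a plastic tip and plastic curettes at implants and a metal tip at teeth. Test patients receive erythritol air-polishing for 5 seconds per site. The same section gives all supragingival debridement to the residents of the Master's programme.
- **VAS collection.** VAS section: "After finishing the supragingival debridement around teeth, another calibrated examiner" hands the patient the scale, "and then perform supragingival debridement around the dental implants and give VAS again". Then: "Patients will be instructed to point at the VAS".

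**The concern.** A double-blind label tells readers that the main comparison is protected from knowledge of the arm. Here the one documented blinded party rates only secondary outcomes. The main outcome is rated by the patient, and no masking of the patient is described. Hypothesis 2 expects superiority on patient-reported outcomes and no difference on clinical outcomes. The described blinding therefore covers the outcomes where no difference is expected and leaves out the one where a difference is. Any reporting influenced by that expectation would favour the test arm. The plan commits to CONSORT reporting, so an unexplained label would probably carry into the publication.

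**Working it through.** **1. Could another procedure supply the second blinded party?**

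| Section | What it provides | Does it mask the VAS comparison? |
|---|---|---|
| Randomization and study groups | Opaque envelopes, opened after hygiene instruction | No. This is concealment before assignment |
| Study Visits; Clinical and VAS examination | Numerical patient code | Protects identity; not said to hide the arm |
| Debridement | Two different devices; no sham or screening described | No |
| VAS | Another calibrated examiner gives the scale | Masking status not stated |
| Follow-up visits | Blinded examiner | Clinical variables only |
| Statistical analysis | Tests listed | No masked analyst described |

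**2. Who debrides the implants?** Debridement says the residents do all of it. Read literally, the VAS section has the examiner who gives the scale then debride the implants and give the scale again. There are three possible readings:

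- The examiner is not a resident. The sections then contradict each other, and the collector knows the arm.
- The examiner is a resident. The sections then agree, but the collector may still be the operator.
- The sentence is loosely drafted. The collector's masking is then still unstated.

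Each reading needs a correction. That patients point at the scale in the collector's presence is a plausible inference; the section does not say who watches or records the score.

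**3. Which comparison is affected?** Hypothesis 2 compares arms, and masking to arm matters there. Hypothesis 1 compares implants with teeth under the conventional ultrasonic device. It is a comparison within patients treated the same way, so masking to arm does not bear on it.

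**4. Arm size.** The Sample Size Calculation uses change in CAL: difference 1 mm, SD 0.9, alpha 0.05, power 80%. Two-sided normal approximation:

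n = 2 × (1.960 + 0.842)² × 0.9² / 1² = 12.7, rounded up to 13 per group.

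With 12% loss: 13 / 0.88 = 14.8, rounded up to 15 per group, 30 in total. This matches the plan. It serves here only as the arm size for step 5.

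**5. Illustration of a reporting shift.** The documents give neither a VAS SD nor a bias size, so both are assumed. The setting is no true effect, 15 per arm and a two-sided t-test at 0.05 (28 degrees of freedom, critical value 2.048). The noncentrality is shift / (SD × √(2/15)).

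| Shift | SD | Noncentrality | Total false positives | Favouring test |
|---|---|---|---|---|
| 0 | any | 0 | 5.0% | 2.5% |
| 0.25 | 1.5 | 0.456 | 7.3% | 6.4% |
| 0.25 | 2.0 | 0.342 | 6.3% | 5.2% |
| 0.25 | 2.5 | 0.274 | 5.8% | 4.5% |
| 0.5 | 1.5 | 0.913 | 14.3% | 14.1% |
| 0.5 | 2.0 | 0.685 | 10.1% | 9.7% |
| 0.5 | 2.5 | 0.548 | 8.3% | 7.6% |

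A Mann-Whitney simulation (20,000 normal trials, shift 0.5) gave 13.1%, 9.2% and 7.7% in total for the three SDs. The shift may come from any source, so these rates do not isolate the part that private scoring would remove.

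**The case against.** **The VAS is self-scored, and the examiner is another person.** Both count in the plan's favour. The word can be read as someone other than the blinded clinical examiner, and self-scoring limits what a collector can do. But self-scoring makes the patient the assessor, and no patient masking is described.

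**Names were removed from the public text.** The unredacted protocol may show who collects the VAS, so the Debridement and VAS point is a request to reconcile. It is not evidence of bias. The conflict in wording remains whoever the person is.

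**Other variables are also called primary.** The Sample Size Calculation names CAL, and Clinical Parameters names dichotomised mBI, as the primary or main variable. The blinded examiner would cover both. This point rests on the outcomes and analysis sections, which both designate the VAS.

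**The figures are chosen inputs.** That is right. Any assumed shift produces inflation, and the range reflects the assumptions.

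**Stronger readings.** A reader might infer that patients were unblinded, that the collector was the operator, or that the VAS results will be biased by a known amount. The documents support none of these. They leave masking undescribed, allow more than one reading of who debrides, and give no basis for sizing a bias. For the same reason, relabelling the trial outright would go too far: a second party may be masked without the plan saying so.

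**Conclusion.** The point holds in a limited form. The plan claims double-blinding, but the only blinding it describes does not reach the between-arm comparison of its main outcome. The sections on debridement and VAS collection must be reconciled. The implant-versus-tooth comparison is not affected.

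No bias size follows from the documents. The rise from 5% to about 8% to 14% rests wholly on an assumed 0.5-point shift, an assumed SD of 1.5 to 2.5, 15 patients per arm and a two-sided test. The plan should be changed on this point, but the finding does not show that the trial's result will be wrong.

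A separate, smaller point concerns compliance, a secondary outcome. Under Compliance Definition, patients who missed a visit because of the lockdown count as compliers if they returned soon after restrictions eased. No time limit is given, the authors decide each case, and masking to arm is not stated. No size can be given, because the number of such patients and their arms are not reported.

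**What to change.** 1. Reconcile the Debridement and VAS sections on who debriding the implants falls to and who collects the VAS. State for patient, operator, VAS collector and clinical examiner whether each is masked.
2. Have patients mark both VAS readings themselves, in private, on a sheet sealed before the operator or collector sees it. This removes collector influence only; it does not stop patients recognising the device.
3. Either name the second blinded party and say how masking is achieved, or describe the trial as examiner-blind for the clinical variables. In the latter case, report possible patient recognition of the device as a limitation of the between-arm VAS comparison.
4. Separately, replace the case-by-case lockdown judgement with one fixed written window after restrictions eased, applied to visit dates with allocation hidden. Add a sensitivity analysis without the credit.

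**Cost:** protocol wording, a VAS sheet with an envelope, and one extra table. The blinding label may become less favourable, and any bias from patients recognising the device would remain and need reporting.
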